4.2.2 Analysis of Secondary Efficacy

MFM (20 or 32)

The Motor function measure (MFM) consists of 32 "Items" (scored 0 to 3) for subjects aged 7 and older (the "MFM 32") or a subgroup of 20 items (scored 0 to 3) that are suitable for small children under the age of 7 (the "MFM 20"). Where summary statistics are required for groups of items, or all of them, the group or grand totals will be expressed as a percentage ("percent outcome") of the maximum possible total for the number of items being aggregated and analyzed. Where the individual items or groups of items are consistent across all subjects, raw item scores (or aggregate sums thereof) will be used, unless specified otherwise below in order to present data in a manner consistent with use of percent outcomes for ease of review.

The MFM consists of three motor function dimensions, Standing and Transfer (D1), Axial and Proximal Motor Function (D2), and Distal Motor Function (D3). A table of each of the 32 items, whether or not it is present in the MFM 20, and its dimension code is provided in Table 4.2-1.

Table 4.2-1. Item definitions for the subscales D1, D2, and D3 of the Motor Function Measure instruments

Item Number	MFM 32	MFM 20	Dimension
1	✓	✓	D2
2	✓		D2
3	✓	✓	D2
4	✓	✓	D3
5	✓	✓	D2
6	✓	✓	D1
7	✓	✓	D2
8	✓		D1
9	✓	✓	D2
10	✓	✓	D2
11	✓	✓	D1
12	✓	✓	D1
13	✓		D2
14	✓	✓	D2
15	✓		D2
16	✓		D2
17	✓		D3
18	✓	✓	D3
19	✓		D3
20	✓		D3
21	✓	✓	D3
22	✓	✓	D3
23	✓	✓	D2
24	✓	✓	D1
25	✓	✓	D1
26	✓		D1
27	✓	✓	D1
28	✓		D1
29	✓		D1
30	✓	✓	D1
31	✓		D1
32	✓	✓	D1

The maximum possible score for the entire group of items and for each of the three dimensions in the MFM 32 and MFM 20 are provided in Table 4.2-2.

Table 4.2-2. Motor Function Measure maximum scores overall and for the subscales

Grouping	MFM 32	MFM 20
Grand Total	96	60
Dimension 1 (D1)	39	24
Dimension 2 (D2)	36	24
Dimension 3 (D3)	21	12

Where summary statistics or hypothesis testing calls for the use of data that spans both MFM 32 and MFM 20 (items present in both MFM 32 and MFM 20 or the use of percent outcomes), all relevant subject data will be used. Where the required data is not part of the MFM 20, only relevant data from the subjects that were assessed with the MFM 32 will be used (see Table 2 and descriptions below).

Summary statistics for the Day 0 assessment (baseline for period 1), the Day 8 assessment, and the corresponding change from baseline (CFB₁) will be presented by treatment, presented by treatment and genetic mutation (data aggregation by both treatment and genetic mutations within each treatment), and separately by treatment and by Pre- and Post-synaptic Mechanism (see Table 2.2-1), for the following MFM Data.

- Total MFM percent outcome, all age groups
- MFM percent outcome for Dimension 1 (D1), all age groups
- MFM percent outcome for Dimension 2 (D1), all age groups
- MFM percent outcome for Dimension 3 (D3), all age groups
- Total MFM percent outcome, ages 2 to less than 17
- MFM percent outcome for Dimension 1 (D1), ages 2 to less than 17
- MFM percent outcome for Dimension 2 (D1), ages 2 to less than 17
- MFM percent outcome for Dimension 3 (D3), ages 2 to less than 17
- Total MFM percent outcome, ages 17 and above
- MFM percent outcome for Dimension 1 (D1), ages 17 and above
- MFM percent outcome for Dimension 2 (D1), ages 17 and above
- MFM percent outcome for Dimension 3 (D3), ages 17 and above
- Each individual item (a total of 32 domains, see Table 3). Where a subject was assessed with the MFM 20 and the individual item is not a component of the MFM 20, that subject will be excluded and any tables and listing of the data will have a foot note indicating that subjects assessed with the MFM 20 have been excluded from that specific table and/or listing. During meetings with the Agency, it was pointed out that MFM might not be completely appropriate for CMS, but was chosen as the only validated, objective assessment of motor function suitable both adult and pediatric subject populations. The analysis of these individual item datasets is intended to fully assess the suitability of the MFM and its component items.

A Mann-Whitney-Wilcoxon test for equality of the CFB for the two treatments in Period 1 for the data types shown above will be presented.

Summary statistics for the Day 21 assessment (baseline for period 2), the Day 29 assessment, and the corresponding change from baseline (CFB₂) for the same MFM datasets analyzed for Period 1 above will also be presented by treatment, presented by

treatment and genetic mutation, and separately by treatment and by Pre- and Post-synaptic Mechanism (see Table 2.2-1).

The change in CFB from Period 1 to Period 2 (the "Individual Treatment Effect") will be computed for each of the MFM datasets described above, with correction for the order of treatment (placebo-amifampridine versus amifampridine-placebo), as needed so that potential effect of the active treatment, using each subject as their own control, can be evaluated. This value estimates

$$\tau_1 - \tau_2$$

where τ_1 represents the treatment effect for each dataset of the Amifampridine Investigational Product Period and τ_2 represents the treatment effect for each dataset of the Placebo Investigational Product Period. A Mann-Whitney-Wilcoxon test of the hypothesis that the above parameter is the same in both treatment sequences will be provided for each dataset. (Note that this is a nonparametric version of the treatment main effect in a linear model without carryover effects or order of treatment effects).

Summary statistics will also be provided for the Individual Treatment Effect derived from the datasets above and will be presented for all relevant subjects by Genetic Defect and separately by Pre- and Post-synaptic Mechanism (see Table 2.2-1). For the MFM individual item analyses results will be sorted by mutation within mutation type and estimated effect size (defined as the estimated difference in the marginal treatment means divided by the standard error of this difference).

The analysis summaries for the above analyses will be sorted by effect size, defined as the T-score associated with the hypothesis test that the difference between treatment group LSMeans is 0.

A mixed effects linear model will be fit to each of the MFM datasets described above with percent outcome or individual item scores (as appropriate for each dataset) as the response variable. The model will include fixed effect terms for treatment, period, age group (2 to less than 6 years, 7 to less than 12 years, 12 to less than 17 years of age, and 17 years of age and above), genetic mutation type (see Table 2.2-1), and sequence*period, where sequence corresponds to the order in which the subject received treatments, and a random effect for subject. No carryover term will be fit. In the case of the MFM percent outcome datasets for the adult only patients, the age group fixed effect term will not be included in the model. The LSMeans for the treatment groups will be calculated and provided, as will the estimated difference along with a 95% confidence interval for this difference and a formal hypothesis test that difference in the means is 0. Note that it is highly likely that some specific mutations will have insufficient subjects to fit the specified model. In that case a notation will be made in the relevant table(s) that there are not sufficient observations to fit the model.

Special care must be taken in crossover designs to ensure that there is no significant carryover effect; however, the pharmacological properties of amifampridine (an elimination half-life of 1.8-2.5 hours) are such that having a 12-day restabilization period will minimize any unequal carryover effects in the analysis.

Clinical Global Impression

CGI-S and CGI-I will be summarized by frequency tables and percentages for each sequence group and period. The values will be analyzed with a Wilcoxon rank-sum test as outlined in Putt and Chinchilli (2004). The treatment effects will be estimated using the Hodges-Lehmann estimator and a 90% asymptotic confidence interval.

Single Fiber Electromyogram

Summary statistics for mean jitter, median jitter, and percent block will be presented by treatment and visit. No formal inferential procedures will be performed for these data.

Slurp Test

Summary statistics for the time to slurp sound from the slurp test and its CFB (Day 0 for Period 1 and Day 21 for Period 2) will be presented. No formal inferential procedures will be performed for these data.

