1.3 Sample Size

The primary analysis variable is the SGI Change from Baseline (CFB). It will be analyzed using the standard analysis for a two-by-two crossover design. The sample size required to control the power depends on the ratio of the between-treatment difference and the standard deviation of the difference (that is, the effect size). Assuming an effect size of 0.5, 23 patients per sequence will ensure power of 90% for the 2-sided test at the 0.05 level.

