4.2 Analysis of Efficacy

4.2.1 Analysis of Primary Efficacy

Summary statistics for the SGI Day 0 assessment (baseline for period 1), SGI Day 8 assessment, and the corresponding change from baseline (CFB₁) will be presented by treatment and by treatment within mutation type (pre- vs. post-synaptic, see Table 2.2-1 above) as period 1. A Mann-Whitney-Wilcoxon test for equality of the CFB₁ in the two treatments in Period 1 will be presented. Summary statistics for the SGI Day 21 assessment (baseline for period 2), SGI Day 29 assessment, and the corresponding change from baseline (CFB₂) will also be presented by treatment and treatment within mutation type as period 2. Also, the change in CFB from Period 1 to Period 2 will be computed. This value estimates

$$\tau_1 - \tau_2$$

where τ_1 represents the treatment effect of the period 1 Investigational Product (IP) and τ_2 represents the treatment effect of period 2 IP. A Mann-Whitney-Wilcoxon test of the hypothesis that the above parameter is the same in both treatment sequences will be provided. Note that this is a nonparametric version of the treatment main effect in a linear model without carryover effects.

A mixed effects linear model will be fit to the data with SGI raw scores as the response. The model will include fixed effect terms for treatment, period, age group (2 to less than 6, 7 to less than 12, and 12 to less than 17 years of age, 17 years and over), mutation type and sequence*period, where sequence corresponds to the order in which the subject received treatments, and a random effect for subject. The LSMeans for the treatment groups will be calculated and provided, as will the estimated difference along with a 95% confidence interval for this difference and a formal hypothesis test that the difference in the means is 0.

Special care must be taken in crossover designs to ensure that there is not significant carryover effect; however, the pharmacological properties of amifampridine are such that

having a 12-day washout period should minimize any unequal carryover effects in the analysis.

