		Day 8	CFB	xxx	xxx	xxx	xxx	xxx	xxx
		Day 21 (Baseline)	RAW	xxx	xxx	xxx	xxx	xxx	xxx
		Day 29	RAW	xxx	xxx	xxx	xxx	xxx	xxx
		Day 29	CFB	xxx	xxx	xxx	xxx	xxx	xxx

^a RAW = observed data entered in the database; CFB = change from baseline = Score at time point - baseline score.
 STATKING Clinical Services (yyyy-mm-dd)
 Source Program: xxxxxxx.sas

Table format repeats for PP population.

Table 7. SGI Score Summary Mann-Whitney Main Effects Test Results
Catalyst Pharmaceuticals, Inc. - CMS-001
FAS Population (N=xxx)

Variable	Test	n	Mean Difference ^a	Test Statistic	P-Value
SGI	Period 1	xx	xxx	xxx	xxx
	Crossover	xx	xxx	xxx	xxx

^a The Period 1 mean-of-differences is the difference in mean CFB at the end of Study Period 1, corresponding to a parallel study design analysis. The Crossover mean-of-differences is the difference between the Period 1 CFB and Period 2 CFB.

STATKING Clinical Services (yyyy-mm-dd)

Source Program: xxxxxxx.sas

Table format repeats for PP population.

Page x of y

Table 9. SGI Score Mixed Model Analysis
Catalyst Pharmaceuticals, Inc. - CMS-001
FAS Population (N=xxx)

Statistic ^a	Amifampridine/ Placebo	Placebo/ Amifampridine
n	xxx	xxx
Least Squares (LS) Mean of Raw SGI Score	xxx	xxx
Between-Treatment Difference in LS Means (Amifampridine - Placebo)	xxx	
Denominator Degrees of freedom	x	
95% CI for Between-Treatment Difference in LS Means (Amifampridine - Placebo)	(xxx, xxx)	

^a Raw SGI score was modeled as the response, with fixed effects terms for treatment, period, age group, mutation type and sequence*period (i.e., carryover). Subject was treated as a random effect.

STATKING Clinical Services (yyyy-mm-dd)

Source Program: xxxxxxx.sas

Table format repeats for PP population.

Table 11. MFM-32 Score Summary Statistics by Treatment, Period and Time Point
 Catalyst Pharmaceuticals, Inc. - CMS-001
 FAS Population (N=xxx)

Treatment	Variable ^a	Period	Time Point	Data Type ^b	Std					
					Mean	Dev	n	Min	Max	Median
Amifampridine/Placebo	xxxxxxxx	1	Day 0 (Baseline)	RAW	xxx	xxx	xxx	xxx	xxx	xxx
			Day 8	RAW	xxx	xxx	xxx	xxx	xxx	xxx
				CFB	xxx	xxx	xxx	xxx	xxx	xxx
	xxxxxxxx	2	Day 21 (Baseline)	RAW	xxx	xxx	xxx	xxx	xxx	xxx
			Day 29	RAW	xxx	xxx	xxx	xxx	xxx	xxx
				CFB	xxx	xxx	xxx	xxx	xxx	xxx
Placebo/Amifampridine	xxxxxx	1	Day 0 (Baseline)	RAW	xxx	xxx	xxx	xxx	xxx	xxx
			Day 8	RAW	xxx	xxx	xxx	xxx	xxx	xxx
				CFB	xxx	xxx	xxx	xxx	xxx	xxx
	xxxxxx	2	Day 21 (Baseline)	RAW	xxx	xxx	xxx	xxx	xxx	xxx
			Day 29	RAW	xxx	xxx	xxx	xxx	xxx	xxx

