				CFB	xxx	xxx	xxx	xxx	xxx	xxx

^a This will correspond to one of the following: Dimension 1, 2, 3, the grand total, the corresponding percentages (X1, X2, X3, X), and the individual item scores.

^b RAW = observed data entered in the database; CFB = Change from baseline = Score at time point - baseline score.

STATKING Clinical Services (yyyy-mm-dd)

Source Program: xxxxxxxx.sas

Table format repeats for PP population.

Table 13. MFM-32 Score Summary Mann-Whitney Main Effects Test Results
 Catalyst Pharmaceuticals, Inc. - CMS-001
 FAS Population (N=xxx)

Scale	Test	n	Mean of Differences ^a	Test Statistic	P-Value
Total	Period 1	xx	xxx	xxx	xxx
	Crossover	xx	xxx	xxx	xxx
D-1	Period 1	xx	xxx	xxx	xxx
	Crossover	xx	xxx	xxx	xxx
D-2	Period 1	xx	xxx	xxx	xxx
	Crossover	xx	xxx	xxx	xxx
D-3	Period 1	xx	xxx	xxx	xxx
	Crossover	xx	xxx	xxx	xxx
Item xx	Period 1	xx	xxx	xxx	xxx
	Crossover	xx	xxx	xxx	xxx
Item yy	Period 1	xx	xxx	xxx	xxx
	Crossover	xx	xxx	xxx	xxx
Item zz	Period 1	xx	xxx	xxx	xxx
	Crossover	xx	xxx	xxx	xxx

^a The Period 1 mean-of-differences is the difference in mean CFB at the end of Study Period 1, corresponding to a parallel study design analysis. The Crossover mean-of-differences is the difference between the Period 1 CFB mean and Period 2 CFB mean. Individual items are sorted by the value of the test statistic associated with the crossover test.

STATKING Clinical Services (yyyy-mm-dd)

Source Program: xxxxxxx.sas

Table format repeats for PP population. Individual items will be ordered in increasing order of the p-values for the Crossover test.

Table 15. MFM-32 Score Mixed Model Analysis
 Catalyst Pharmaceuticals, Inc. - CMS-001
 FAS Population (N=xxxx)

Variable	Statistic ^a	Amifampridine/ Placebo	Placebo/ Amifampridine
Overall	n	xxx	xxx
	Least Squares (LS) Mean of Change from Baseline	xxx	xxx
	Between-Treatment Difference in LS Means (A-B)	xxx	
	Denominator degrees of freedom	x	
	95% CI for Between-Treatment Difference in LS Means (A-B)	(xxx, xxx)	
D1 Domain	n	xxx	xxx
	Least Squares (LS) Mean of Change from Baseline	xxx	xxx
	Between-Treatment Difference in LS Means (A-B)	xxx	
	Denominator degrees of freedom	x	
	95% CI for Between-Treatment Difference in LS Means (A-B)	(xxx, xxx)	
D2 Domain	n	xxx	xxx
	Least Squares (LS) Mean of Change from Baseline	xxx	xxx
	Between-Treatment Difference in LS Means (A-B)	xxx	
	Denominator degrees of freedom	x	
	95% CI for Between-Treatment Difference in LS Means (A-B)	(xxx, xxx)	
D3 Domain	n	xxx	xxx

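### The MFM crossover rank test in SAP 4.2.2 tests the period effect, not treatment, and the Crossover mean difference in Tables 7, 13 and 21 cancels the treatment effect

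*SAP*

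**What the plan says.** **SGI (SAP 4.2.1).** The within-patient quantity is the change from baseline (CFB) in Period 1 set against that in Period 2. Its two terms are the effects of whichever product was given in Period 1 and in Period 2. A Mann-Whitney-Wilcoxon test compares this quantity between the two sequences.

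**MFM (SAP 4.2.2).** The same difference is named the Individual Treatment Effect, but it is computed "with correction for the order of treatment (placebo-amifampridine versus amifampridine-placebo), as needed so that potential effect of the active treatment" can be evaluated with each patient as their own control. The terms are redefined to match: the first "represents the treatment effect for each dataset of the Amifampridine Investigational Product Period" and the second is the placebo counterpart, whatever the order of treatment. The between-sequence test is kept: "A Mann-Whitney-Wilcoxon test of the hypothesis that the above parameter is the same in both treatment sequences will be provided for each dataset". The SAP then adds: "Note that this is a nonparametric version of the treatment main effect in a linear model without carryover effects or order of treatment effects".

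**Table shells (SAP Appendix B).** Each scale has a row labelled Crossover with one mean difference, one test statistic and one p-value. The Table 7 footnote (SGI) reads "The Crossover mean-of-differences is the difference between the Period 1 CFB and Period 2 CFB". The footnotes to Tables 13 and 21 (MFM-32 and MFM-20) read "The Crossover mean-of-differences is the difference between the Period 1 CFB mean and Period 2 CFB mean". None of them mentions a change of sign by sequence or a contrast between sequences.

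**The concern.** In a two-by-two crossover, a between-sequence comparison isolates treatment only when the within-patient difference is taken in period order, because treatment then enters the two sequences with opposite signs. Re-signing the difference to drug minus placebo gives treatment the same sign in both, and a between-sequence test then removes it. SAP 4.2.2 does both.

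MFM is named in the primary efficacy objective (Protocol 9.1, SAP 1.1), although its analysis is secondary. Protocol 15.8 promises the standard two-by-two crossover analysis for it, which this is not. The rule covers 12 summary datasets (total and three dimensions, in three age groupings) and 32 individual items. The shells also order items by the crossover test result. Items could therefore be ranked by period effect in an analysis meant to judge whether MFM suits this disease.

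The printed mean is a separate fault. A single Period 1 minus Period 2 mean over all patients averages a positive and a negative treatment effect, so it says almost nothing about the drug. For SGI it stands beside the primary endpoint's p-value.

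**Working it through.** **Inputs.** SAP 1.3 gives effect size 0.5 (treatment difference over the SD of the difference), two-sided 0.05, 23 patients per sequence and 90% power: "Assuming an effect size of 0.5, 23 patients per sequence will ensure power of 90% for the 2-sided test at the 0.05 level". SAP 1.1 gives 1:1 allocation and up to 23 subjects in all; a split of 12 and 11 is my assumption. The period effects used below are illustrative, since the documents give none.

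**The plan's own figure.** Treat the crossover as a two-sample comparison of Period 1 minus Period 2 differences, with SD 1 and contrast 2 × 0.5 = 1.
- 23 per sequence: noncentrality 1/√(1/23 + 1/23) = 3.39, 44 df, power 0.913 (0.900 at 22 per sequence). The stated 90% is reproduced with the uncorrected, between-sequence form.
- 12 and 11: noncentrality 1/√(1/12 + 1/11) = 2.40, 21 df, power 0.63.

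**Algebra of the test.** Let δ be amifampridine minus placebo, π the Period 1 minus Period 2 shift, AP the amifampridine-first sequence and PA the placebo-first sequence.

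| Quantity compared | AP mean | PA mean | Contrast, AP − PA |
|---|---|---|---|
| Uncorrected CFB1 − CFB2 (SGI form) | δ + π | −δ + π | 2δ |
| Order-corrected (MFM form) | δ + π | δ − π | 2π |

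In the MFM form a constant δ shifts every patient equally, so the ranks and the p-value do not change. In one simulated data set the p-value was 0.2815 when δ was shifted by 0, 0.5, 2 and 10 SD.

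**Simulation** (normal differences with SD 1, 5,000 runs per row, Mann-Whitney test at 0.05):

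| Patients | δ | π | SGI form rejects | MFM form rejects |
|---|---|---|---|---|
| 23 + 23 | 0.5 | 0 | 89.1% | 5.0% |
| 23 + 23 | 1 | 0 | 100% | 5.1% |
| 23 + 23 | 2 | 0 | 100% | 4.7% |
| 23 + 23 | 0 | 0.5 | 4.8% | 89.4% |
| 12 + 11 | 0.5 | 0 | 59.3% | 4.2% |
| 12 + 11 | 1 | 0 | 99.0% | 4.7% |
| 12 + 11 | 2 | 0 | 100% | 4.2% |
| 12 + 11 | 0 | 0.5 | 4.5% | 59.2% |

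**Algebra of the printed mean.** The Period 1 minus Period 2 mean over all patients has expectation

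[n_AP(δ + π) + n_PA(−δ + π)]/N = π + δ(n_AP − n_PA)/N.

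- 23 + 23: π exactly.
- 12 + 11: π + δ × 1/23 = π + 0.043δ. A true effect of 0.5 SD with no period effect would appear as about 0.02.
- Half the between-sequence contrast: [(δ + π) − (−δ + π)]/2 = δ at any allocation.

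**The case against.** The strongest reply is that SAP 4.2.2 is muddled rather than settled. It starts from the change between periods, applies the correction only where needed, and says that a treatment main effect is intended. The footnotes to Tables 13 and 21 use the uncorrected difference. A programmer could follow the shells, or copy the SGI wording, and run a valid test. It is also true that, for MFM, both faults arise together only if the test and the mean beside it use different variables: the order-corrected values give a bad test but a valid mean, and the uncorrected values give the reverse.

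This is fair about what might be programmed, but it does not rescue the text. The definitions of the two terms fix the order-corrected reading, and on that reading the algebra is not in dispute. If the shells govern instead, text and shells contradict each other, and the choice decides whether the p-value concerns the drug or the period. For MFM, each consistent choice leaves either the test or the mean wrong.

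Other points stand as limits:
- The SGI rank test and its p-value are correctly specified. Only the printed mean in Table 7 is at fault, and Table 5 gives the means from which the right contrast can be computed.
- The shells do not say in words that the mean is pooled over sequences. That follows from a single value with no contrast defined.
- MFM also has a Period 1 rank test, which does address treatment but uses only half the crossover. The mixed model is not a clean fallback: it fits treatment, period and sequence-by-period together, and its fixed-effect rank is 4 with or without treatment, so treatment is aliased as written. That is a separate matter.

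**Conclusion.** The concern holds. As written, the MFM crossover rank test carries no information on a constant treatment effect: it rejects at about the nominal 5% however large the effect when there is no period effect, and it responds to a period effect as strongly as a valid test would to a treatment effect of the same size. The Crossover mean in Tables 7, 13 and 21, read literally, estimates the period effect plus at most a small remnant of the treatment effect: none with equal sequences, about 4% of it at 12 and 11, and more if completion is unbalanced.

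The cancellation is algebraic and does not depend on normal data. It assumes an additive treatment effect that is the same in both sequences; unequal carryover would also enter the MFM contrast. The rejection rates rest on normal differences, the assumed 12 and 11 split, and an illustrative period effect of 0.5 SD. I rate this as a must-fix because the rule is wrong as written for an endpoint in the primary objective, and the correct form already stands in SAP 4.2.1.

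**What to change.** 1. In SAP 4.2.2, apply the Mann-Whitney-Wilcoxon test to the uncorrected CFB1 minus CFB2 by sequence, as 4.2.1 does for SGI. Keep the order-corrected Individual Treatment Effect for descriptive summaries only. At an effect of 0.5 SD with no period effect, this raises the rejection rate from 5.0% to 89.1% with 23 per sequence, and from 4.2% to 59.3% with 12 and 11.
2. In Tables 7, 13 and 21 and their per-protocol repeats, define the Crossover estimate as half the between-sequence difference in mean CFB1 minus CFB2, signed amifampridine minus placebo. Half the Hodges-Lehmann shift between sequences would be an equally acceptable companion to a rank test; the SAP already uses that estimator for CGI.
3. State the direction of the difference in Data Listings 18 and 19 as well. Their Treatment Main Effect Difference is also taken between Day 8 and Day 29 changes, so its sign depends on sequence, and Listing 19 is sorted on it.

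The cost is one paragraph of SAP text, three table footnotes and two listing footnotes. No change to data collection or trial conduct is needed.

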2.0 Data Analysis Considerations

2.1 Types of Analyses

The term summary statistics for quantitative data refers to the following list of statistics unless otherwise specified: n (number of non-missing observations), mean, standard deviation, minimum, median, and maximum. Categorical variables will be summarized with frequency counts and percentage of the relevant group. Summary statistics will be summarized by treatment sequence and study period. Unless otherwise stated, all hypotheses will be tested at a two-sided $\alpha = 0.05$ significance level

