	Least Squares (LS) Mean of Change from Baseline	xxx	xxx
	Between-Treatment Difference in LS Means (A-B)	xxx	
	Denominator degrees of freedom	x	
	95% CI for Between-Treatment Difference in LS Means (A-B)	(xxx, xxx)	

^a MFM score expressed as a percentage of the maximum possible was modeled as the response, with fixed effects terms for treatment, period, sequence*period (i.e., carryover) and mutation type at Baseline. Individuals measured with the MFM-20 (i.e., aged 2- <7 years) are excluded from the analyses for items in the MFM-32 excluded from the MFM-20.

STATKING Clinical Services (yyyy-mm-dd)

Source Program: xxxxxxx.sas

Table format repeats for PP population. Parts will be included for all subjects, pre- and post- synaptic mutations and each mutation type. Individual items will be ordered in increasing order of the p-values for the Crossover test.

Page x of y

Table 33. Clinical Global Impression Summary by Mutation Type
 Catalyst Pharmaceuticals, Inc. - CMS-001
 FAS Population (N=xxx)

Part x of y: xxxxxxxxxxxx Mutation

Variable	Treatment Sequence	Time Point	Type ^a	1	2	3	4	5	6	7
CGI-Severity	Amifampridine/Placebo	Day 0 (Baseline)	RAW	xxx						
		Day 8	RAW	xxx						
			CFB	xxx						
		Day 21	RAW	xxx						
			CFB	xxx						
		Day 29	RAW	xxx						
			CFB	xxx						
		Day 0 (Baseline)	RAW	xxx						
		Day 8	RAW	xxx						
			CFB	xxx						
		Day 21	RAW	xxx						
			CFB	xxx						
		Day 29	RAW	xxx						
			CFB	xxx						
CGI-Improvement	Amifampridine/Placebo	Day 0 (Baseline)	RAW	xxx						
		Day 8	RAW	xxx						
			CFB	xxx						
		Day 21	RAW	xxx						
			CFB	xxx						
		Day 29	RAW	xxx						
			CFB	xxx						
		Day 0 (Baseline)	RAW	xxx						
		Day 8	RAW	xxx						
			CFB	xxx						
		Day 21	RAW	xxx						
			CFB	xxx						
		Day 29	RAW	xxx						
			CFB	xxx						

^a RAW = observed data entered in the database; CFB = change from baseline = Value at timepoint - Baseline value.

STATKING Clinical Services (yyyy-mm-dd)

Source Program: xxxxxxxx.sas

Table format repeats for PP population. Parts will be included for all subjects, pre- and post- synaptic mutations and each mutation type.

Table 35. Clinical Global Impression Score Mann-Whitney Main Effects Analysis
 Catalyst Pharmaceuticals, Inc. - CMS-001
 FAS Population (N=xxxx)

Subgroup	Variable	Time Point	Hodges-Lehmann Estimate	90% Confidence Limits	Mann-Whitney Test P-value
All Subjects	CGI-Severity	Day 8	xxxx	(xxxx, xxxx)	xxxxxx
		Day 21	xxxx	(xxxx, xxxx)	xxxxxx

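### CGI treatment effects get a 90% interval beside a test at two-sided 0.05, and the SAP gives no reason for the different level

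*SAP*

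**What the plan says.** On the CGI scales, SAP 4.2.2 states: "The values will be analyzed with a Wilcoxon rank-sum test as outlined in Putt and Chinchilli (2004"). For the treatment effects it then specifies the "Hodges-Lehmann estimator and a 90% asymptotic confidence interval". It names no significance level for the test and gives no reason for the interval level.

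SAP 2.1 supplies the default: "Unless otherwise stated, all hypotheses will be tested at a two-sided" level of 0.05. Nothing in the CGI paragraph states otherwise, so 0.05 applies.

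The Table 35 shell in SAP Appendix B repeats the choice. Its column "90% Confidence Limits" stands directly before the Mann-Whitney p-value, for all subjects and for each mutation subgroup. The same format serves the per-protocol version, Table 36. Text and shell agree, so 90% is not a slip in one place.

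The other efficacy intervals are at 95%. For SGI, SAP 4.2.1 promises "the estimated difference along with a 95% confidence interval for this difference"; for MFM, SAP 4.2.2 promises the "estimated difference along with a 95% confidence interval for this difference and a formal hypothesis test that difference in the means is 0".

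Protocol 15.6 plans summary statistics only for CGI, so the CGI test and its interval are additions made in the SAP.

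**The concern.** A reader of Table 35 will take the interval and the p-value as two views of one result. They are set at different levels: the interval belongs to a two-sided 0.10 test, while the p-value is judged at 0.05. A limit above zero could then sit beside a result that the plan calls not significant, and the interval could be read as evidence that the test did not give.

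The CGI intervals would also carry a lower confidence level than the SGI and MFM mixed-model intervals in the same report. A reader comparing precision across endpoints may miss this. A 90% interval can be right for an equivalence question or a one-sided test, but the SAP states neither for CGI.

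**Working it through.** **Inputs.** CGI interval level 90% (SAP 4.2.2, Table 35). Test level two-sided 0.05 (SAP 2.1). CGI scale 1 to 7, whole numbers (Protocol 10.7.3, Appendices 3 and 4). Number of patients: up to 23 in all (SAP 1.1) or 23 per sequence, so 46 (SAP 1.3); both are shown. CGI variability and effect size are not in the documents, so those below are assumptions.

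**Step 1: the test that the interval matches.** Implied two-sided level = 1 − 0.90 = 0.10, with critical value 1.645. The 0.05 test uses 1.960. Width ratio on the normal approximation: 1.645 / 1.960 = 0.84, so about 16% narrower.

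**Step 2: chance of disagreement if the data were continuous.** Let Z be normal with mean d√N and variance 1, where d is the treatment difference divided by the SD of the within-patient difference. The interval excludes zero with p ≥ 0.05 when 1.645 ≤ |Z| < 1.960.

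The plan has no CGI figure to reproduce. As a check on the set-up, d = 0.5 with N = 46 gives power of 92.4% (normal) or 91.3% (noncentral t, 44 df), against the 90% that SAP 1.3 states for SGI.

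| d | N | 90% interval excludes 0 | p < 0.05 | Disagreement |
|---|---|---|---|---|
| 0 | either | 10.0% | 5.0% | 5.0% |
| 0.25 | 46 | 52.1% | 39.6% | 12.5% |
| 0.25 | 23 | 33.0% | 22.4% | 10.6% |
| 0.5 | 46 | 96.0% | 92.4% | 3.6% |
| 0.5 | 23 | 77.4% | 66.9% | 10.5% |

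Simulated rank-sum tests with the asymptotic Hodges-Lehmann interval on continuous data (1,500 runs per scenario) agree: 4.8% with no effect (23 + 23 patients) and 10.9% at d = 0.5 (12 + 11). A 95% interval never excluded zero with p ≥ 0.05 in those runs.

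**Step 3: a case on 7-point ratings.** Take differences between two ratings, 12 patients against 11:

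- x: 0, 0, 0, 0, 0, 0, 1, 2, 2, 2, 3, 3
- y: −5, −4, −3, −2, −1, −1, −1, 1, 1, 3, 3

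Of the 12 × 11 = 132 pairwise differences x − y, 32 are negative, 6 are zero and 94 are positive. So U = 94 + 6/2 = 97, against 132/2 = 66 under no effect. The tie-corrected SD is about 16.02, so z = 31 / 16.02 = 1.94 and p = 0.0529.

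For the interval, the SD without tie correction is √(132 × 24 / 12) = 16.25. The lower limit is the ordered difference of rank 66 − 1.645 × 16.25 = 39.3, so the 39th; at 95% it is 66 − 1.960 × 16.25 = 34.2, so the 34th. The 39th is 1 and the 34th is 0. The 90% interval is (1, 4) and the 95% interval is (0, 4). The 90% interval excludes zero although the test is not significant at 0.05.

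**Step 4: how often on 7-point ratings.** Ratings were simulated as independent normals, rounded and cut to 1–7, with rating SD 1.0, 1.5 or 2.5 and a treatment shift of 0.6 SD (period means 4 ± 0.3 SD). There were 6,000 runs per scenario.

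| Patients | SD | 90% interval excludes 0, p ≥ 0.05 | p < 0.05, 90% interval includes 0 |
|---|---|---|---|
| 12 + 11 | 1.0 | 0% | 16.8% |
| 12 + 11 | 1.5 | 0.08% | 8.6% |
| 12 + 11 | 2.5 | 0.55% | 4.0% |
| 23 + 23 | 1.0 | 0% | 29.6% |
| 23 + 23 | 1.5 | 0% | 14.6% |
| 23 + 23 | 2.5 | 0.02% | 7.2% |

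Heavy ties put limits exactly on zero. This makes the disagreement of Step 2 rare and the opposite one common.

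**The case against.** The level is disclosed in both the text and the column heading, and SAP 2.1 governs hypothesis tests without fixing an interval level. CGI is secondary with no success criterion attached, and the p-value does not depend on the interval. All of this stands and limits the weight of the point. It does not supply a reason for 90%, nor does it bring the interval into line with the test beside it.

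A reader might infer that every CGI result with p between 0.05 and 0.10 will show an interval clear of zero. The documents do not support this: CGI is a whole-number 7-point scale, and the percentages in Step 2 belong to continuous data. Likewise, 16% is a normal-theory ratio. In the Step 3 example the widths are 3 and 4, a 25% difference, and in other samples the two intervals may coincide.

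A reader might also infer that CGI uncertainty is understated against every other efficacy endpoint. SAP 4.2.2 gives the single fiber EMG and Slurp tests no inference, and the SGI and MFM Mann-Whitney shells (Tables 7, 13 and 21) print no interval. The comparison holds only against the SGI and MFM mixed-model intervals.

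Finally, a wider interval cannot cure the opposite mismatch: any 90% interval that includes zero still includes it at 95%. That is correct.

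**Conclusion.** The point holds as a consistency fault in secondary reporting. The CGI interval is set at a level that matches a 0.10 test, beside a p-value judged at 0.05 and unlike the 95% mixed-model intervals, without explanation. Nominal non-coverage is 10% instead of 5%. The interval can exclude zero beside a non-significant test, as the worked example shows, but on tied 7-point ratings this should be rare (0 to 0.6% in the scenarios tried).

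The frequencies rest on assumed effect sizes, SDs, independence within patient and group sizes; the mismatch of levels rests only on the SAP text. The primary SGI analysis is untouched, and so is every CGI p-value.

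**What to change.** Change 90% to 95% in the Clinical Global Impression paragraph of SAP 4.2.2 and in the Table 35 column heading, which Table 36 inherits. If 90% was deliberate, give the reason in SAP 4.2.2 and footnote the tables to say that the interval does not correspond to the 0.05 test.

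The cost is two edits and wider CGI intervals, by about 19% on the normal approximation (1.960 / 1.645 = 1.19). Data collection, tests and the primary analysis stay as they are. Because ties can still leave the interval touching zero beside a significant test, a short footnote saying so would help the reader.
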